# **Research Objectives and Specific Aims:**

Diabetes is arguably the most urgent healthcare challenge of the 21st century. An estimated that 1 in 11 adults have diabetes with an estimated 415 million individuals with diabetes worlwide. In the United States, 21 million persons have been diagnosed with diabetes, with approximately 90–95% of cases due to type 2 diabetes (T2D). Diabetes is a leading cause of cardiovascular disorders, blindness, end-stage renal failure, and non-traumatic amputations. Extensive evidence from epidemiological and randomized control studies have shown that improved glycemic control decreases the risk of diabetic complications, and is likely to be of benefit in preventing long-term cardiovascular complications. However, despite the availability of a large variety of antidiabetic drugs, insulin formulations, and clinical guidelines, only one-third of patients on basal insulin and one-fourth of those on basal insulin and oral antidiabetes drugs achieved target A1C <7.0%.

Poor adherence to insulin regimens is common and reported in up to two-third of patients with diabetes.The most common barriers with insulin injections are socio-economic factors, complexity of treatment and adherence to prescribed dosing time, which lead to frequent insulin omissions, as reported in more than half of patients with diabetes. The frequency of insulin injection irregularities (omission, mistiming and dosing) are similar for patients using basal insulin alone versus those using basal with bolus insulin regimens. Thus it is important to identify patients at risk and to develop strategies and tools to increase adherence to prescribed insulin regimens. Recent advances in this field include the availability of electronic reminders, mobile communication technology such as phone short message services,  smartphones and wrist-worn smartwatch,  and a variety of insulin pens with memory functions and electronic display. However, current devices are designed for specific insulin brands, are not interchangeable among available insulin pens, and they lack alarm systems to notify patients and caretakers about insulin delays and missing doses.

Insulclock®15 is a small electronic device easily plugged to any brand of insulin pen devices to help track date, time and dosage of the last injection, type of insulin used and temperature. Insulclock has an alarm system with visual and sound alerts to prevent insulin omissions and mistiming. Via Bluetooth and smart-phone technology, information is stored and readily available for data analysis by patients, caregivers and healthcare professionals. The Insulclock's real time memory and alert system are likely to improve treatment adherence, patient's satisfaction, and quality of life measures, which may improve glycemic control in insulin treated patients with T2D.

# **Study Aims:**

Aim 1. To determine whether the Insulclock system results in improved treatment adherence and reductions in treatment irregularities (insulin omission, mistiming and dosing) compared to conventional insulin pen device. Patients with inadequately controlled T2D treated with oral antidiabetic agents and basal insulin (NPH, glargine or detemir) will be randomized to Group A: Insulclock device with feedback or to Group B: Insulclock without feedback. All patients will use the Insulclock device attached to glargine U100 insulin pens (SoloStar®) during the study period. Participants in Group A will receive daily information on their smartphone on insulin administration (time and dosing) as well as reminders in the event of missing doses. Participants in Group B, will use the Insulclock, but will not receive feedback on insulin administration. Differences in insulin injection irregularities (omission, mistiming and dosing) will be compared at each clinic visit during the study period.

**Hypothesis:** The Insulclock device will improve adherence reducing insulin omission, mistiming and dosing errors compared to standard pen device.

Aim 2. To determine whether the Insulclock system yields higher treatment satisfaction scores in poorly controlled patients with T2D compared to a conventional insulin pen device. Patients with inadequately controlled T2D (HbA1c  $\geq$  7.0%) treated with oral antidiabetic agents and basal insulin once daily (NPH, glargine or detemir) will be enrolled in a 24 week randomized, cross-over clinical trial comparing the

use of Insulclock device system vs standard insulin pen. Treatment satisfaction will be assessed with the Diabetes Treatment Satisfaction Questionnaire Status (DTSQs) to be administered at baseline (week 0) and at weeks 12 and 24 to assess relative changes in the DTSQ between interventions. The amplitude of the score on the DTSQc gives the degree of change in satisfaction while the direction (positive or negative) will provide guidance on the preference of therapy.

**Hypothesis:** The Insulclock device will improve treatment satisfaction compared to standard insulin pen device.

**Aim 3.** To explore whether changes in adherence with the Insulclock improves glycemic control, as measure by change in HbA1c from baseline, when compared to conventional insulin pen device. HbA1c will be measured at week 0 and at weeks 12 and 24 to assess differences in glycemic control between groups. **Hypothesis:** The Insulclock device by improving treatment adherence may improve glycemic control compared to standard pen device.

# II. BACKGROUND AND STATUS OF WORK IN THE FIELD.

### **Basal Insulin therapy in Type 2 Diabetes**

Insulin is the oldest and the most potent agent for the treatment of diabetes. Insulin therapy is the treatment of choice for patients with severely elevated HbA1c and symptoms of hyperglycemia,  and in patients with inadequate glycemic control despite treatment with OADs and non-insulin injectables. Clinical guidelines recommend the use of basal insulin, given once (glargine, detemir, degludec) or twice daily (neutral protamine Hagedorn [NPH], detemir) as add-on to non-insulin agents. Basal insulin analogs are preferred over NPH insulin because a single basal dose provides a relatively flat serum insulin concentration for up to 24 hours. Newer basal insulin formulations – glargine U300 and degludec- have more prolonged and stable pharmacokinetic (PK) and pharmacodynamic (PD) characteristics than glargine U100 and detemir. Despite of the multiple basal insulin formulations, a systematic review of 218 randomized clinical trials found that only 39% of patients with T2D treated with basal insulin achieve an HbA1c <7%. Moreover, a recent study reported no overall improvements in glycemic control among patients with T2D during the past decade.

### **Insulin Non-Adherence**

Poor adherence to medical treatment is a significant contributor to negative outcomes and increased risk of morbidity in patients with diabetes. Insulin non-adherence has been reported in up to two-thirds of patients, with approximately one-third reporting an average of three episodes of insulin omission/non-adherence within the previous month. Regimen complexity, in terms of the number of the treatments and frequency of administration, is known to have a negative impact on adherence. Brod et al  reported that most missed or mistimed doses were unintentional (~80%). The most common barriers with insulin injections are socio-economic factors, complexity of treatment and adherence to prescribed dosing time, which lead to frequent insulin omission reported in more than half of patients with diabetes. The insulin tracking and alert system will address the issue of nonadherence by reminding patients about insulin dosing and avoiding missing insulin injections. The alarm system can be programmed at any time(s) of the day alerting patients and caretakers on delayed injections, which may reduce missing doses.

# Use of Insulin Pens and Patient Satisfaction

Multiple studies have reported that insulin pen devices are associated with greater treatment satisfaction and patient preference as well as improved dose accuracy compared to the traditional vial/syringe. Standardized assessments of treatment satisfaction, including the Diabetes Treatment Satisfaction Questionnaires (DTSQs and DTSQc) and the Insulin Delivery System Rating Questionnaire (IDSRQ), have been validated and tested for reliability. Some insulin pen studies have evaluated patient satisfaction with these tools. Improving treatment satisfaction can lead to improvements in quality of life. Improvements in quality of life are often cited as leading to greater adherence to treatment protocols and insulin administration.

# **Advances in Insulin Treatment**

Like most areas of medicine, treatment of diabetes has changed considerably over the past decade because of technological advances including glucose monitoring and insulin delivery options. Major advances to improve adherence in diabetes include the availability of mobile communication technology such as phone short message services,  electronic reminders, smartphones and wrist-worn smartwatches,  and a variety of insulin pens with memory functions and electronic display.

Examples of smart pens commercially available or in development:

**Easylog**, a compact add-on module designed to fit pen injectors. Smart sensors collect injection data directly from disposable or reusable pen and connect to smartphones via Bluetooth.

**Datapen**, a Smart reusable injector pen connected to a mobile app. Each injection can be tracked and Bluetooth technology to allow access treatment data from mobile phone.

**Smartplus Insulin Pen**, an injection delivery compatible with insulin pen needle device that supports insulin cartridges from Eli Lilly and Sanofi-Aventis insulin formulations. The pen stores and displays 195 injection doses, including the date and time of the injection.

KiCoPen captures dose delivered and sends the information to an associated smartphone app.

Human Pen Memoir® (Eli Lilly & Co) and NovoPen5® (Novo Nordisk) durable insulin pens with the addition of a memory function that records the dose of and hours passed since the last injection.

**Insulclock**® is a small electronic device which is plugged to all pen devices allowing tracking information on date, time, dose of the last injection, remaining insulin in the pen device, as well as type of insulin used and temperature. Insulclock has an alarm/reminder system with visual and acoustic alerts to reduce insulin omissions and mistiming. Via Bluetooth and smart-phone technology, information is store and readably available for data analysis by patients, caregivers and healthcare professionals.

**Significance and Innovation: In the US,** all patients with type 1 diabetes are treated with basal insulin alone and about 30% of patients with type 2 diabetes are treated with basal insulin alone or in combination with oral agents to achieve and maintain glycemic control. About 30.3% of patients on basal insulin and 24.2% of those on basal insulin and oral antidiabetes drugs achieved target A1C <7.0%. A systematic review of 218 randomized trials reported that 39% of patients with T2D treated with basal insulin achieve an HbA1c <7%. Insulin non-adherence is reported in up to two-thirds of patients, with one-third reporting an average of three episodes of insulin omission/non-adherence within the previous month.

Recent devices have become available to improve adherence to insulin therapy in diabetes include the availability of mobile communication technology such as phone short message services, electronic reminders, smartphones and wrist-worn smartwatch, and a variety of insulin pens with memory functions and electronic display. However, these devices are not interchangeable among different insulin pens and they do not have the alarm systems to notify patients and caretakers about insulin delays and missing doses. The insulin tracking and alert system may be of great help in reminding patients about insulin dosing and avoiding missing insulin injections. In addition, the Insulclock will also allow us to assess treatment nonadherence. Differences in treatment adherence before and after the crossed over will provide objective evidence of compliance and treatment adherence.

# **III. Research Design and Methods**

# **Study Aims:**

Aim 1. To determine whether the Insulclock system results in improved treatment adherence and reductions in treatment irregularities (insulin omission, mistiming and dosing) compared to conventional insulin pen device.

# Aim 2. To determine whether the Insulclock system yields higher treatment satisfaction scores in poorly controlled patients with T2D compared to a conventional insulin pen device.

Aim 3. To explore whether changes in adherence with the Insulclock system results in improved glycemic control, as measure by change in HbA1c from baseline, when compared to conventional insulin pen device.

Study Rationale. Poor adherence to medical treatment is common and is associated with increased risk of morbidity in patients with diabetes. Insulin non-adherence has been reported in up to two-thirds of patients, with approximately one-third reporting an average of three episodes of insulin omission/nonadherence within the previous month. Regimen complexity, in terms of the number of the treatments and frequency of administration, is known to have a negative impact on adherence. Patients with irregular mealtime and active social-work schedule were more likely to have insulin irregularities, many of them intentional omissions. In patients with T1D, poor adherence is the main cause of hyperglycemic crises accounting for more than half of admissions with hyperglycemic crises. Several devices have been designed to improve insulin adherence including new delivery options like smart pens with memory functions and electronic display; however they have significant limitations and their efficacy in improving treatment adherence or in improving glycemic control have not been tested in rigorous randomized clinical trials. The Insulclock device allows to record date, time, dose of the last injection, as well as type of insulin used, and remaining insulin volume in the pen device. A major advance of Insulclock over available smart pens is its ability to send visual and acoustic alert message directly from the device or via text to patients and caretakers in the event of insulin omissions and mistiming. In addition, the large volume data storage will allow patients and healthcare providers to download information on insulin patterns and omissions over a long period, allowing for a better understanding of insulin adherence. The present study will test whether the Insulclock improves adherence, quality of life, treatment satisfaction, and glycemic control compared to the standard pen device.

# **Study Objectives:**

# **Primary Objective.**

To demonstrate the superiority of Insulclock in treatment adherence (insulin omission, mistiming and dosing) over conventional insulin injection pen devices.

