# Methods:

This will be a randomized (1:1), controlled, 26-week cross-over clinical trial in patients with inadequately controlled T2D (HbA1c  $\geq$  7.0% to  $\leq$  12.0%) while treated with oral antidiabetic agents and basal insulin (NPH, glargine or detemir). Participants will be randomized to use the Insulclock device (Group 1) and standard of care using an insulin pen device (Group 2). All patients will use the Insulclock device attached to glargine U100 insulin pens (SoloStar®) during the study period. During the study period. Participants in Group 1 will receive daily information on their smartphone on insulin administration (time and dosing) as well as reminders in the event of missing doses. Participants in Group 2, will use the Insulclock, but will not receive feedback on insulin treatment or alerts.

Randomization will be stratified by:

• HbA1c at Screening (<8.0%, >8.0%)

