One week after screening and before randomization, eligible participants will receive an Insulclock device. They will be properly trained on how to use it, charge and connect Insulclock to their mobile devices. Insulcloud will make smartphone available for subjects, who do not own a smartphone, during the course of the study. Technique skills such as the ability to navigate the app, press the button for 5 seconds while giving insulin injection, and how to connect the device to their phones will be explained. They will be asked to use the Insulclock with their insulin pen, to get familiarized with it. An assessment will be done after the week of using the device in order to review quality and understanding of the technology. Those subjects that fail to use the device properly will be deemed Screen Failures.

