### Analysis of Primary Endpoint:

The primary outcome of treatment adherence with the use of Insulclock with feedback or no information (blinded) is whether a patient has a good adherent to the treatment regimen (assessed based on insulin omission, mistiming, and dosing). Given the 2 by 2 cross-over design, the superiority of the Insulclock system over the conventional insulin pen device will be determined by comparing the percent of patients showing a good treatment adherence with Insulclock but a poor treatment adherence with the conventional device to the percent of patients showing a poor treatment adherence with Insulclock but a good treatment adherence with the conventional device. We will perform this comparison based on McNemar's test assuming the period effect is negligible. We will further conduct logistic regression to accommodate potential period effect and adjust for other potential confounders. We will apply standard model selection and model checking procedures (such as the Hosmer-Lemeshow tests) to decide and evaluate the final model. A p value of <0.05 will be considered significant.

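### Insulclock is on every pen in both randomized periods and only feedback and alerts differ, so the trial does not directly test the stated superiority or non-inferiority against a conventional pen

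*Combined protocol and SAP*

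**What the plan says.** The Primary Objective is "To demonstrate the superiority of Insulclock in treatment adherence (insulin omission, mistiming and dosing) over conventional insulin injection pen devices". The Secondary Objectives seek non-inferiority to a standard pen on satisfaction, quality of life, adherence and glycemic control. Analysis of Primary Endpoint says that "the superiority of the Insulclock system over the conventional insulin pen device will be determined by comparing the percent of patients" in the two discordant categories, using McNemar's test.

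Methods introduces the arms this way: "Participants will be randomized to use the Insulclock device (Group 1) and standard of care using an insulin pen device (Group 2"). It then says "All patients will use the Insulclock device attached to glargine U100 insulin pens", and "Participants in Group 2, will use the Insulclock, but will not receive feedback on insulin treatment or alerts". Aim 1 describes the same control: "Participants in Group B, will use the Insulclock, but will not receive feedback on insulin administration". Assessment of Results, and the opening of Analysis of Primary Endpoint, likewise describe the outcome under Insulclock with feedback or with none.

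Before randomization every eligible patient receives the device. Study Visits says "They will be properly trained on how to use it, charge and connect Insulclock to their mobile devices", and "They will be asked to use the Insulclock with their insulin pen, to get familiarized with it".

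**The concern.** The plan names one comparator and delivers another. Group 2 is labelled as usual care with a pen, but its patients inject with a pen that carries Insulclock, as Group 1 does. What is switched at crossover is the feedback and the alerts.

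If the text is followed as written, a significant McNemar result will be reported as superiority of Insulclock over a conventional pen. It would show that feedback and alerts help patients who already have the device attached. The secondary objectives are more exposed. A non-inferiority statement on satisfaction or quality of life against a standard pen would rest on a comparison in which the inconvenience of the device is the same on both sides. A device that patients find a nuisance could look acceptable because it was never set against a pen without it.

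**Working it through.** **1. Content of the two conditions (Study Aims, Methods).**
- With feedback: glargine pen + attached Insulclock + feedback/alerts.
- Without feedback: glargine pen + attached Insulclock.
- Difference: feedback/alerts only.

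**2. Statements that name a conventional or standard pen as comparator.**

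| Place | Count |
|---|---|
| Study Aims: Aims 1 and 2 with hypotheses | 5 |
| Aim 3 with hypothesis | 2 |
| Research Design and Methods: Aim 1 restated | 1 |
| Aims 2 and 3 restated, end of Study Rationale | 3 |
| Primary Objective | 1 |
| Secondary Objectives | 1 |
| Methods (Group 2 label) | 1 |
| Statistical Analysis, opening | 1 |
| Analysis of Primary Endpoint | 3 |
| Analysis of Secondary Endpoints | 1 |
| Power Considerations | 1 |
| **Total** | **20** |

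**3. What the randomized data identify.** Let F, S and C be the mean outcome (for adherence, the proportion with good adherence) with feedback Insulclock, silent Insulclock and a conventional pen. Then

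F − C = (F − S) + (S − C).

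The trial estimates F − S. In the plan's notation this is Ptp × p − Ptp × (1 − p) = Ptp × (2p − 1). For example, Ptp = 60% and p = 0.8 give 0.60 × 0.60 = 0.36. No randomized period observes C, so S − C is not estimated. To read F − S as the size of F − C requires S = C. To carry only the direction across requires that any S − C below zero be smaller than the gain F − S. The document states neither assumption.

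**4. Data outside the randomized periods.** Study Visits describes the switch to the SoloSTAR pen and the issue of diaries under Visit 1, and the issue of Insulclock one week after screening. This suggests about one week of pen use without the device, though the switch date is not given. Any such data would be short, non-randomized and recorded in patient diaries, whereas the primary outcome is registered by the device.

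**5. Effect on the power figures.** None on the arithmetic.
- Evaluable pairs: (40 + 40) × 0.85 = 68.
- Discordant pairs: 68 × Ptp, rounded. Test: two-sided exact binomial of p = 0.5 at alpha 0.05 (the plan does not state sidedness; two-sided reproduces its table).

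| Ptp | 90% | 80% | 70% | 60% | 50% |
|---|---|---|---|---|---|
| Discordant pairs | 61 | 54 | 48 | 41 | 34 |
| Power at p = 0.7, recomputed | 87.9% | 83.7% | 74.9% | 66.5% | 55.4% |
| Power at p = 0.7, plan | 87.9% | 83.7% | 74.9% | 66.5% | 55.4% |

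- Continuous secondary outcomes: SD of the difference = √(2 × (1 − 0.3)) = 1.183 SD; 0.41 / 1.183 = 0.3465; the paired t-test with 68 pairs has 80.4% power, in line with the plan's figure of over 80%.

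The figures stand. What needs stating is that Ptp and p describe feedback versus no feedback.

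**The case against.** The best defence is that the control is fully disclosed and sensible. Irregularities are registered by the device, so a control group without it would lack that record, and a silent logger is a reasonable way to obtain it. The background and rationale also attribute the expected benefit to the real-time memory, reminders and alerts. Feedback and alerts are what Group 2 does not receive, so for adherence a silent device is a natural no-intervention control, and the pen wording can be taken as shorthand.

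Much of this stands. It justifies the design, and it makes the assumption S = C more plausible for adherence than for other outcomes. It does not state or support that assumption, and shorthand in the objective and the primary analysis becomes the trial's conclusion. Nor does it reach satisfaction and quality of life, which the logger does not measure.

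A reader might infer more than the documents support:
- *That no information at all exists on a pen without Insulclock.* This is too absolute, given the apparent week before the device is issued.
- *That every satisfaction assessment follows device use.* The DTSQs is listed with the preparation for Visit 2, but the text does not say when it is completed, so this remains an inference.
- *That the bias can be sized in SD units.* The document gives no basis for any range. Its 0.41 SD is a detectable difference for continuous secondary outcomes in general, not an expected effect of the device.

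**Conclusion.** The point holds as a mismatch between the stated comparator and the randomized one. In both randomized periods the contrast is feedback/alerts on versus off with Insulclock attached. Twenty statements name a conventional or standard pen instead, and the primary and secondary objectives and the primary analysis draw superiority or non-inferiority against it. The unobserved part, silent Insulclock versus pen, cannot be estimated from the randomized data, and its direction is unknown for adherence: being monitored could raise it, and the burden of the device could lower it. The gap matters most for satisfaction and quality of life.

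It would be wrong to conclude that the randomized comparison is invalid or the power calculation faulty. The comparison is sound for the effect of feedback and alerts, and the power figures reproduce. This rests on reading Methods literally, that every patient has the device on the pen in both periods, which Aim 1, Assessment of Results and Analysis of Primary Endpoint all bear out.

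**What to change.** - **Aims, hypotheses, last sentence of Study Rationale, both sets of objectives, the Group 2 label in Methods, and the opening of Statistical Analysis:** restate the comparison as *Insulclock with feedback/alerts versus Insulclock without feedback/alerts*.
- **Analysis of Primary Endpoint:** for example, *Superiority of Insulclock with feedback/alerts over Insulclock without them will be assessed by comparing the percentage of patients with good adherence with feedback/alerts but poor adherence without, against the percentage with the reverse pattern.*
- **Analysis of Secondary Endpoints and Power Considerations:** replace the conventional device with *Insulclock without feedback/alerts*, and state that the Ptp and p scenarios refer to that contrast. They form a grid of scenarios, so there is no single projection to re-justify.
- **Conclusions:** draw none against a conventional pen from the randomized data. Stating the silent-device assumption openly is possible but weaker, because the randomized data cannot check it and the week before device issue is too limited to support it.

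The cost is the rewording of 20 statements and a narrower claim. Visits, sample size, the primary test and the power arithmetic do not change. Whether a paired t-test suits the comparison of period differences in Analysis of Secondary Endpoints is a separate matter that this rewording does not settle.
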